3.2. Efficacy

Summary and analyses for primary efficacy data, secondary efficacy data and exploratory efficacy data, unless indicated in Section 3.2.1 below, will not be presented for the final analysis except for HIV Drug Resistance data from Modified Treated Subjects who underwent resistance testing will be summarized and presented, see additional details in Section 3.4.

Subject data listings will be provided for primary efficacy data, secondary efficacy data, exploratory efficacy data, and available plasma concentration data based on Treated Subjects population in Sections 3.2.2 and 3.2.3.

3.2.1. Tables

Number	Title	BMS Table number/File Name/BMS Template
2.1	Detailed Summary of HIV-1 RNA < 40 c/mL Proportion of Responders at Week 24 Snapshot Modified Treated Subjects	Table S.5.1.1A / rt-vl-resp40w24s1.lst / SS_VL_T_001
2.2	Summary of HIV-1 RNA < 40 c/mL Proportion of Responders by Scheduled Assessments Over Time Modified Treated Subjects (Observed) ¹	Table S.5.1.1E / rt-vl-resp40w24obssubgs1.lst / SS_VL_T_003 (By Weeks 24, 48, and 96 instead of By Subgroup)
2.3	Summary Statistics for Values and Change from Baseline Over Time CD4 Cell Count (cells/uL) Modified Treated Subjects (Observed) ¹	Table S.5.7.1A / rt-lb-cd4s1.lst / SS_VL_T_006 (Without “By Subgroup”)
2.4	Summary Statistics for Values and Change from Baseline Over Time CD4 Cell Percentage Modified Treated Subjects (Observed) ¹	Table S.5.8.1A / rt-lb-cd4pcts1.lst / SS_VL_T_006 (Without “By Subgroup”)

Number	Title	BMS Table number/File Name/BMS Template
---------------	--------------	--

1 Add the following footnote to the tables 2.2-2.4:

Note: Modified Treated Subjects (Observed): Consisting of subjects in the Treated Subjects Population excluding subjects who have no HIV-1 RNA result data in the assessment visit windows due to discontinuation and who discontinued on or after the date of site notification of study termination by the sponsor [October 10, 2016], will be used to evaluate efficacy in a sensitivity analysis.

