2. FINAL ANALYSIS

Per the company decision to end this study prior to all subjects reaching the primary endpoint, a simplified approach for the final report has been proposed by the project team. Hence the final analyses for AI468048 study as described in this appendix will be performed on subjects who were enrolled into this study, regardless of study stage, and will supersede what have been previously stated in the finalized BMS RAP Version 2.0. In addition, due to the GCP non-compliance of Site $\frac{PP}{D}$ ([name] in Chile) with ICH GCP E6 (R2) Guidelines, data obtained from this GCP non-compliant site will not be included in the final analyses (e.g., summary tables of selected efficacy and safety data); however, subject data listings will include all subjects enrolled in this study. Subject data listings for the GCP non-compliant Site $\frac{PP}{D}$ will also be provided.

The details of the final reporting and analysis plan are described as below:

1) Analysis Populations

Due to the GCP non-compliance of Site $\frac{PP}{D}$ data obtained from this GCP non-compliant site will be excluded in the final analyses.

Populations for Analyses for this synoptic report are defined as follows:

- Enrolled subjects are those who signed an informed consent form and were assigned a Patient Identification number (PID).
- Randomized subjects are enrolled subjects who received a treatment assignment from the IVRS and will be used in subject data listings as specified.
- Modified Randomized Subjects are enrolled subjects who received a treatment assignment from the IVRS, excluding subjects from Site $\frac{PP}{D}$. The modified randomized subjects will be used to assess subject disposition.
- Treated Subjects are randomized subjects who received at least 1 dose of study therapy and will be used in subject data listings as specified.
- Modified Treated Subjects are randomized subjects who received at least 1 dose of study therapy, exclude subjects from Site $\frac{PP}{D}$. Modified treated subjects will be used to assess demography and baseline characteristics,

protocol deviations, exposure, concomitant medication, efficacy, resistance and safety data.

- Pharmacokinetic (PK) population is defined as all treated subjects who have any available concentration-time data. The evaluable PK population is a sub-population including all treated subjects who have adequate PK profiles.

2) Demographic and baseline characteristic

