This report includes the analyses of demographics, baseline characteristics, and baseline resistance data based on Modified Treated Subjects population. Subject data listings will be based on Treated Subjects population.

The detailed outputs for demographic and baseline characteristic data are listed in the Section 3.1 of List of Displays for Study Population.

3) Simplified report on primary efficacy endpoint

Selected summaries and analyses on primary efficacy endpoint will be performed for this final analysis, based on Modified Treated Subjects population. Subject data listings will be based on Treated Subjects population.

The detailed outputs for primary efficacy endpoint data are listed in the Section 3.2 of List of Displays for Efficacy.

4) Secondary and Exploratory Efficacy Endpoints

Analyses for secondary and exploratory efficacy endpoints, including pharmacokinetic and quality of life endpoints, will not be performed except for HIV-1 RNA, CD4+ counts, and drug resistance endpoints (see additional details in Section 3.4, Virology) which are subject to availability of the data and will be analyzed based on Modified Treated Subjects population. There will be no subgroups and no multivariate analysis performed for secondary and exploratory efficacy endpoints for this final analysis. Subject data listings based on Treated Subjects population except PK data which will be based PK population.

The detailed outputs for primary secondary and exploratory efficacy endpoints are listed in the Section 3.2 of List of Displays for Efficacy.

5) Safety displays

Final safety analysis will be summarized based on Modified Treated Subjects population; however, subject data listings will be based on Treated Subjects population. Subject data listings will be based on Treated Subjects population.

The detailed outputs are listed in the Section 3.3 of List of Displays for Safety.

6) Virology

HIV drug resistance data will be summarized based on Modified Treated Subjects population. Subject data listings will be based on Treated Subjects population.

The detailed outputs for HIV drug resistance data are listed in the section of List of Display for Virology.

7) General

The display for TLFs will be based on BMS shells and will not utilize HARP for SAC.

The list of displays has been updated as shown below.

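### The footnote to Tables 2.2–2.4 of the final-analysis appendix builds Modified Treated Subjects (Observed) on the wrong parent population and omits the exclusion of the GCP non-compliant site

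*SAP*

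**What the plan says.** The final-analysis appendix to the SAP, which supersedes the earlier plan for the final report, sets the site exclusion in Section 2. The opening paragraph says that data from the non-compliant site "will not be included in the final analyses (e.g., summary tables of selected efficacy and safety data"). Item 1 (Analysis Populations) repeats that "data obtained from this GCP non-compliant site will be excluded in the final analyses". Item 1 then defines two treated sets. The first, Treated Subjects, takes in everyone who was randomized and dosed, at every site, and is meant for the listings. The second leaves the site out: "Modified Treated Subjects are randomized subjects who received at least 1 dose of study therapy, exclude subjects from Site" (identifier redacted). This second set is assigned to the summaries, with efficacy, resistance and safety among them.

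Item 4 (Secondary and Exploratory Efficacy Endpoints) says that the retained HIV-1 RNA, CD4+ and resistance endpoints "will be analyzed based on Modified Treated Subjects population".

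Section 3.2.1 lists four efficacy tables. Table 2.1, the Week 24 snapshot, is on Modified Treated Subjects. Tables 2.2 to 2.4 are titled Modified Treated Subjects (Observed) and carry a footnote that defines the set. Its opening words are "Consisting of subjects in the Treated Subjects Population excluding subjects who have no HIV-1 RNA result data in the assessment visit windows". The rest of the footnote limits that exclusion to gaps caused by stopping, and to subjects who stopped no earlier than 10 October 2016, when sites were told that the sponsor was ending the study. The footnote adds that the set serves a sensitivity analysis of efficacy. It does not mention the site.

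**The concern.** In this appendix Treated Subjects is a defined term. It includes the non-compliant site and is reserved for listings. The footnote takes that set as the base for three efficacy summaries. The Analysis Populations list defines no Observed set, so the footnote is the only place from which a programmer can take one.

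Two things are at stake. If the footnote is followed, data that the appendix says must not enter the efficacy summaries enter the observed HIV-1 RNA and CD4 tables, under a title that says they are not there. If the title is followed, the report carries a footnote that describes a different population from the one tabulated. Two programmers working independently could each follow one of these texts and obtain different denominators.

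**Working it through.** No figure in the plan is in dispute, so the check compares the definitions as sets.

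**Inputs**

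- T: Treated Subjects, all randomized and dosed subjects (appendix Section 2, item 1).
- S: members of T at the non-compliant site.
- M: Modified Treated Subjects = T without S (same item).
- D: members of T with no HIV-1 RNA in the assessment window because of discontinuation, who discontinued on or after 10 October 2016 (footnote to Tables 2.2–2.4).

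**The set as the footnote writes it**

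F = T without D.

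**The set that the titles and Section 2 imply**

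O = M without D = T without S and without D.

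**Difference**

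F without O = members of S who are not in D. These are treated subjects at the excluded site who have HIV-1 RNA in the window, or who stopped before 10 October 2016, or who are otherwise not caught by the discontinuation condition. F and O coincide only if every treated subject at the site falls in D, and nothing in the document says so.

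**Consequence for Table 2.2 against Table 2.1 at Week 24**

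| Comparison | Set for Table 2.1 | Set for Table 2.2 | What differs |
|---|---|---|---|
| Titles and Section 2 followed | M | M without D | D removed |
| Footnote followed | M | T without D | D removed, and site subjects not in D added |

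In the first row the two tables differ only in how discontinuation around the termination notice is handled, which is what the footnote's exclusion addresses. In the second row a change of site is mixed in. This comparison exists only for Table 2.2 at Week 24, because Table 2.1 is a Week 24 table. Tables 2.3 and 2.4 are CD4 summaries and have no snapshot counterpart. For them the consequence is only that the excluded site would be included.

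**Size**

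The number of subjects in S, and how many of them are in D, would be needed. The document gives neither, nor the final arm sizes, so no shift in a response rate or CD4 mean can be calculated.

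**The case against.** The strongest reply is that this is one missing word. Section 2 states the site exclusion twice, assigns efficacy to Modified Treated Subjects and repeats this for HIV-1 RNA and CD4+, and all three table titles agree. The appendix also mixes the terms elsewhere: the title of Table 3.15 refers to 5 percent of Treated Subjects and then names Modified Treated Subjects as its population. A programmer working from the titles would leave the site out. All of this stands. It shows that the intended base can be recovered, and that nobody chose to include the site.

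It does not remove the problem. The footnote is the operative definition of a set that is defined nowhere else, and the appendix orders it to be printed on the tables. It is therefore wrong on the page whichever text is followed.

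Two stronger readings are tempting, and the document does not support them.

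- A reader might infer that the reported tables will contain the non-compliant data. That follows only if the footnote is followed over the titles and Section 2, and most of the text points the other way.
- A reader might put a size on the effect. Assume an arm of 40 (the planned size), 80% response at the other sites (the rate the SAP expects overall) and s site subjects among the 40. The rate then lies between 0.8 × (40 − s)/40 and (0.8 × (40 − s) + s)/40: 76–81% for s = 2, 72–82% for s = 4 and 68–83% for s = 6. These limits rest on invented site sizes, on a planned arm size in a study that was stopped early, and on every site subject failing or every one responding. If the site also responded at 80%, the shift would be zero. The range says nothing about the likely effect.

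**Conclusion.** The inconsistency is real and can be read directly from the text. The footnote to Tables 2.2–2.4 names the unmodified Treated Subjects as its base and has no site exclusion. This contradicts the titles of those tables, the exclusion of the site in Section 2, and the rule in item 4 of that section for HIV-1 RNA and CD4+.

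The reach is limited. Table 2.1, which carries the primary endpoint, does not have the footnote and is untouched. The SAP describes an estimation study, and the list of final efficacy tables contains no futility test, so no formal decision depends on Tables 2.2–2.4. The numerical effect is unknown and could be nil.

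This should be fixed, as a reconciliation of a population definition. The document does not support treating it as evidence that excluded data will be reported. The conclusion assumes only that Treated Subjects carries its defined meaning in the footnote.

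**What to change.** Change the base named in the footnote so that it opens with: subjects in the Modified Treated Subjects population (excluding the GCP non-compliant site). Leave the discontinuation condition as it is. Program Tables 2.2, 2.3 and 2.4 from that set. It would also help to add Modified Treated Subjects (Observed) to the Analysis Populations list in Section 2, so that the set is defined once and the footnote only repeats it.

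The cost is one phrase in the footnote and one population flag in the programs. No new data are needed, and Table 2.1 and the listings do not change.

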3.2.2. ICH Listings

Number	Title	BMS Table number/File Name/BMS Template
7	Listing of Outcomes from HIV-1 RNA < 40 c/mL Snapshot Analysis Data for Subjects in the Week 24 Snapshot Treated Subjects	Appendix 5.1.1A / rl-vl-outcome24s1.lst / SS_VL_L_004

3.2.3. Other Listings

Number	Title	BMS Table number/File Name/BMS Template
32	Listing of HIV-1 RNA Treated Subjects	Appendix 5.1.1D / rl-vl-vl1.lst / SS_VL_L_005
33	Listing of CD4+ and CD8+ T- Cell Count and Percentages Treated Subjects	Appendix 5.1.1E / rl-lb-cd4cd81.lst / SS_VL_L_005
34	Listing of BMS-955176 Plasma Concentration – Time Data PK Population	Appendix 8.2.1A / rl-pk-cpar1bmss1.lst / MS_PK_L_001
35	Listing of ATV Plasma Concentration – Time Data PK Population	Appendix 8.2.1B / rl-pk-cpar1atvs1.lst / MS_PK_L_001

Number	Title	BMS Table number/File Name/BMS Template
36	Listing of DTG Plasma Concentration – Time Data PK Population	Appendix 8.2.1C / rl-pk-cpar1dtgs1.lst / MS_PK_L_001

3.3. Safety

The Modified Treated Subjects population will be used in the safety summaries and analyses. All treated subjects will be used in the data listings. Subject data listings will be based on Treated Subjects population.

3.3.1. Tables

Number	Title	BMS Table number/File Name/BMS Template
3.1	Extent of Exposure to BMS-955176 Time on Therapy Modified Treated Subjects	Table S.4.1.1A / rt-ex-bmss1.lst / SS_EX_T_001
3.2	Extent of Exposure to Tenofovir Time on Therapy Modified Treated Subjects	Table S.4.1.1B / rt-ex-tdfs1.lst / SS_EX_T_001
3.3	Extent of Exposure to Atazanavir Time on Therapy Modified Treated Subjects	Table S.4.1.1C / rt-ex-atvs1.lst / SS_EX_T_001
3.4	Extent of Exposure to Dolutegravir Time on Therapy Modified Treated Subjects	Table S.4.1.1D / rt-ex-dtgs1.lst / SS_EX_T_001
3.5	Extent of Exposure to Ritonavir Time on Therapy Modified Treated Subjects	Table S.4.1.1E / rt-ex-rtvs1.lst / SS_EX_T_001
3.6	Extent of Exposure to Treatment Regimen Time on Therapy Modified Treated Subjects	Table S.4.1.1F / rt-ex-regimens1.lst / SS_EX_T_001
3.7	Adverse Events Overall Adverse Events Summary Modified Treated Subjects	Table S.6.7.1 rt-ae-overallsums1.lst SS_AE_T_001
3.8	Summary of Serious Adverse Events Modified Treated Subjects	Table S.6.2.1A / rt-ae-saes1.lst / GS_AE_T_X_001
3.9	Summary of Serious Adverse Event With Death As An Outcome Modified Treated Subjects	Table S.6.2.1C / rt-ae-saeldeaths1eu.lst / GS_AE_T_X_001

CONFIDENTIAL

AI468038/205891

Number	Title	BMS Table number/File Name/BMS Template
3.10	Summary of Drug Related Serious Adverse Event With Death As An Outcome Modified Treated Subjects	Table S.6.2.2D / rt-ae-relsaedeaths2eu.lst / GS_AE_T_X_001
3.11	Listing of Serious Adverse Events Modified Treated Subjects	Table S.6.2.1E / rl-ae-saes1.lst / GS_AE_L_S_001
3.12	Death Listing Enrolled Subjects	Table S.6.1.1 / rl-ae-deaths1.lst / SS_AE_L_001
3.13	Summary of Adverse Events Leading to Discontinuation of Study Medication Modified Treated Subjects	Table S.6.3.1A / rt-ae-aediscs1.lst / GS_AE_T_X_001
3.14	Listing of Adverse Event Leading to Discontinuation of Study Medication Modified Treated Subjects	Table S.6.3.1C / rl-ae-discs1.lst / GS_AE_L_X_001
3.15	Summary of Non-Serious Adverse Events Occurring in at Least 5 Percent of Treated Subjects Modified Treated Subjects	Table S.6.5.1A / rt-ae-nsae5pcts1.lst / GS_AE_T_X_001
3.16	Summary of Grade 1 to 4 Adverse Events Modified Treated Subjects	Table S.6.5.1B / rt-ae-grade1to4s1.lst / GS_AE_T_X_001
3.17	Summary of Grade 2 to 4 Adverse Events Modified Treated Subjects	Table S.6.5.1C / rt-ae-grade2to4s1.lst / GS_AE_T_X_001
3.18	Summary of Grade 3 to 4 Adverse Events Modified Treated Subjects	Table S.6.5.1D / rt-ae-grade3to4s1.lst / GS_AE_T_X_001
3.19	Summary of Grade 1 to 4 Related Adverse Events Modified Treated Subjects	Table S.6.5.1E / rt-ae-relateds1.lst / GS_AE_T_X_001

CONFIDENTIAL

AI468038/205891

Number	Title	BMS Table number/File Name/BMS Template
3.20	Summary of Grade 2 to 4 Related Adverse Events Modified Treated Subjects	Table S.6.5.1F / rt-ae-relgrade2to4s1.lst / GS_AE_T_X_001
3.21	Summary of Grade 3 to 4 Related Adverse Events Modified Treated Subjects	Table S.6.5.1G / rt-ae-relgrade3to4s1.lst / GS_AE_T_X_001
3.22	Summary of CDC Class C AIDS Events Modified Treated Subjects	Table S.6.4.1A / rt-ae-cdcaes1.lst / GS_AE_T_X_001
3.23	Listing of Adverse Event CDC Class C AIDS Events Modified Treated Subjects	Table S.6.4.1B / rl-ae-cdcaes1.lst / GS_AE_L_X_001
3.24	Summary of Gastrointestinal Events of Special Interest Modified Treated Subjects	Table S.6.4.1C / rt-ae-giaes1.lst / GS_AE_T_X_001
3.25	Listing of Adverse Event Gastrointestinal Events of Special Interest Modified Treated Subjects	Table S.6.4.1D / rl-ae-giaes1.lst / GS_AE_L_X_001
3.26	Summary of Worst Toxicity Grade Modified Treated Subjects	Table S.7.1.1A / rt-lb-toxs1.lst / SS_LB_T_001
3.27	Summary of Grade 3-4 Toxicity Modified Treated Subjects	Table S.7.1.1B / rt-lb-g34toxs1.lst / SS_LB_T_001
3.28	Summary of Treatment-Emergent Abnormalities Modified Treated Subjects	Table S.7.1.1C / rt-lb-etoxs1.lst / SS_LB_T_001
3.29	Summary Statistics for Renal Function Values and Change from Baseline - SI Units Modified Treated Subjects	Table S.7.2.1A / rt-lb-renals1.lst / SS_VL_T_006

CONFIDENTIAL

AI468038/205891

Number	Title	BMS Table number/File Name/BMS Template
3.30	Summary Statistics for Renal Function Values and Change from Baseline - US Units Modified Treated Subjects	Table S.7.2.1B / rt-zl-renals1.lst / SS_VL_T_006
3.31	Summary Statistics for Fasting Lipid Values and Change from Baseline - SI Units Modified Treated Subjects	Table S.7.2.1C / rt-lb-lipidss1.lst / SS_VL_T_006
3.32	Summary Statistics for Fasting Lipid Values and Change from Baseline - US Units Modified Treated Subjects	Table S.7.2.1D / rt-zl-lipidss1.lst / SS_VL_T_006
3.33	Summary Statistics for Fasting Lipid Values and Percent Change from Baseline - SI Units Modified Treated Subjects	Table S.7.2.1E / rt-lb-pchglipidss1.lst / SS_VL_T_006
3.34	Summary Statistics for Fasting Lipid Values and Percent Change from Baseline - US Units Modified Treated Subjects	Table S.7.2.1F / rt-zl-pchglipidss1.lst / SS_VL_T_006
3.35	Summary Statistics for Renal Biomarker Values and Change from Baseline - US Units Modified Treated Subjects	Table S.7.5.1A / rt-zl-bmrenals1.lst / SS_VL_T_006
3.36	Summary Statistics for Renal Biomarker Values and Change from Baseline - SI Units Modified Treated Subjects	Table S.7.5.1B / rt-lb-bmrenals1.lst / SS_VL_T_006
3.37	Summary Statistics for Renal Biomarker Values and Percent Change from Baseline - US Units Modified Treated Subjects	Table S.7.5.1C / rt-zl-pchbmrenals1.lst / SS_VL_T_006

CONFIDENTIAL

AI468038/205891

Number	Title	BMS Table number/File Name/BMS Template
3.38	Summary Statistics for Renal Biomarker Values and Percent Change from Baseline - SI Units Modified Treated Subjects	Table S.7.5.1D / rt-lb-pchbmrenals1.lst / SS_VL_T_006
3.39	Summary Statistics for Bone Biomarker Values and Change from Baseline - US Units Modified Treated Subjects	Table S.7.5.1E / rt-zl-bmbones1.lst / SS_VL_T_006
3.40	Summary Statistics for Bone Biomarker Values and Change from Baseline - SI Units Modified Treated Subjects	Table S.7.5.1F / rt-lb-bmbones1.lst / SS_VL_T_006
3.41	Summary Statistics for Bone Biomarker Values and Percent Change from Baseline - US Units Modified Treated Subjects	Table S.7.5.1G / rt-zl-pchbmbones1.lst / SS_VL_T_006
3.42	Summary Statistics for Bone Biomarker Values and Percent Change from Baseline - SI Units Modified Treated Subjects	Table S.7.5.1H / rt-lb-pchbmbones1.lst / SS_VL_T_006
3.43	Summary of Electrocardiogram Values and Changes from Baseline over Time Modified Treated Subjects	Appendix 7.3.1A / rt-eg-sumchgs1.lst / SS_EG_T_003
3.44	Summary of Electrocardiogram Change from Baseline Category Modified Treated Subjects	Appendix 7.3.1B / rt-eg-changecats1.lst / SS_EG_T_001
3.35	Summary of Electrocardiogram Category Modified Treated Subjects	Appendix 7.3.1C / rt-eg-cats1.lst / SS_EG_T_002

Number	Title	BMS Table number/File Name/BMS Template
3.46	Summary of Vital Sign Values and Changes from Baseline over Time Modified Treated Subjects	Appendix 7.4.1A / rt-vs-sums1.lst / SS_VL_T_006

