7.6.1 Overall Adverse Events

Adverse events will be classified by primary System Organ Class (SOC) and Preferred Term (PT) according to the latest version of the Medical Dictionary for Regulatory Activities (MedDRA) in production at BMS at the time of database lock.

AEs and SAEs with an onset on or after the start of study therapy through 30 days after the last dose of study therapy will be considered as occurring during study therapy. These will be summarized and presented by SOC and PT both in descending order of frequency over all treatment arms, unless otherwise specified.

Table 7.6.1-1: Adverse Event Summaries

Endpoint	During Study Therapy	During Study Therapy, after Switch to Continuation Dose
SAEs	X	X
SAEs leading to death ^a	X	
SAEs related to study therapy and leading to death ^a	X	
Non-SAEs ≥ 5% ^a	X	
AEs leading to discontinuation of study therapy	X	X
AEs - All Grades	X	
AEs - Grade 2 to 4	X	
AEs- Grade 3 to 4	X	

Table 7.6.1-1: Adverse Event Summaries

Endpoint	During Study Therapy	During Study Therapy, after Switch to Continuation Dose
Related AEs - All Grades	X	
Related AEs - Grade 2 to 4	X	
Related AEs - Grade 3 to 4	X	
CDC Class C AIDS Events	X	
Events of Special Interest	X	
Exposure-adjusted Events $\geq 5\%$	X	
Exposure-adjusted SAEs ^a	X	
Exposure-adjusted SAEs related to study therapy ^a	X	
Exposure-adjusted non-SAEs $\geq 5\%$ ^a	X	

a ClinicalTrials.gov or EudraCT reporting requirement

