7.6.12 Multiple Adverse Events

Several descriptive summaries of adverse events that take into account the number of occurrences that an AE was reported by individual subjects will be provided. In order to prepare these summaries, the CRF data will be processed according to standard BMS algorithms to categorize each line of subject data as a new occurrence or a continuation of an existing event.

This determination will be based upon onset and resolution dates. Each line of subject data will represent the maximum severity observed as well as the last known assessed relationship to study medication by the investigator.

This data will be presented as the rate per 100 years of patient exposure. Exposure to study medication will be calculated according to approved standard BMS algorithms as well.

As an example, if 5 subjects report 7 unique episodes of headache and had a combined cumulative exposure of 20 years to study medication, the incidence rate is reported as $7 / 20 * 100$ or 35 cases per 100 patient years of exposure.

For adverse events with multiple occurrences, the following will be provided:

- A table showing the total number and rate (exposure adjusted) of occurrences for general AEs occurring in at least 5% of the subjects treated.
- A listing displaying the unique instances of all AEs (i.e., after duplicates have been eliminated and overlapping and contiguous occurrences of the same event have been collapsed).

Exposure-adjusted summaries will also be provided for SAEs, SAEs related to study therapy and non-SAEs.

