365	Table S.6.5.2G	rt-ae-relgrade3to4s2.lst	GS_AE_T_X_001	Adverse Event Summary Grade 3 to 4 Related Adverse Events Treated Subjects - Stage 2	WK24S2, WK48S2, WK96S2
366	Appendix 6.5.1	rl-ae-lists1.lst	GS_AEL_X_001	Adverse Event Treated Subjects - Stage 1	WK24S1, WK48S1, WK96S1, WK96S2
367	Appendix 6.5.2	rl-ae-lists2.lst	GS_AEL_X_001	Adverse Event Treated Subjects - Stage 2	WK24S2, WK48S2, WK96S2
368	Table S.6.4.1A	rt-ae-cdcaes1.lst	GS_AE_T_X_001	Adverse Event Summary CDC Class C AIDS Events Treated Subjects - Stage 1	WK24S1, WK48S1, WK96S1, WK96S2
369	Table S.6.4.2A	rt-ae-cdcaes2.lst	GS_AE_T_X_001	Adverse Event Summary CDC Class C AIDS Events Treated Subjects - Stage 2	WK24S2, WK48S2, WK96S2
370	Table S.6.4.3A	rt-ae-cdcaes12.lst	GS_AE_T_X_001	Adverse Event Summary CDC Class C AIDS Events Treated Subjects - Stage 1 and 2	WK96S2
371	Table S.6.4.1B	rl-ae-cdcaes1.lst	GS_AEL_X_001	Adverse Event CDC Class C AIDS Events Treated Subjects - Stage 1	WK24S1, WK48S1, WK96S1, WK96S2
372	Table S.6.4.2B	rl-ae-cdcaes2.lst	GS_AEL_X_001	Adverse Event CDC Class C AIDS Events Treated Subjects - Stage 2	WK24S2, WK48S2, WK96S2
373	Table S.6.4.1C	rt-ae-giaes1.lst	GS_AE_T_X_001	Adverse Event Summary Gastrointestinal Events of Special Interest Treated Subjects - Stage 1	WK24S1, WK48S1, WK96S1, WK96S2
374	Table S.6.4.2C	rt-ae-giaes2.lst	GS_AE_T_X_001	Adverse Event Summary Gastrointestinal Events of Special Interest Treated Subjects - Stage 2	WK24S2, WK48S2, WK96S2
375	Table S.6.4.3C	rt-ae-giaes12.lst	GS_AE_T_X_001	Adverse Event Summary Gastrointestinal Events of Special Interest Treated Subjects - Stage 1 and 2	WK96S2
376	Table S.6.4.1D	rl-ae-giaes1.lst	GS_AE_L_X_001	Adverse Event Gastrointestinal Events of Special Interest Treated Subjects - Stage 1	WK24S1, WK48S1, WK96S1, WK96S2

No.	Table No.	Output File Name	Template ID	Title and Population	Purpose
377	Table S.6.4.2D	rl-ae-giaes2.lst	GS_AE_L_X_001	Adverse Event Gastrointestinal Events of Special Interest Treated Subjects - Stage 2	WK24S2, WK48S2, WK96S2
378	Table S.6.6.1A	rt-ae- expadjusts1.lst	GS_AE_T_M_001	Exposure Adjusted Adverse Events Summary Treated Subjects - Stage 1	WK24S1, WK48S1, WK96S1, WK96S2
379	Table S.6.6.2A	rt-ae- expadjusts2.lst	GS_AE_T_M_001	Exposure Adjusted Adverse Events Summary Treated Subjects - Stage 2	WK24S2, WK48S2, WK96S2

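### The final-analysis appendix drops every exposure-adjusted adverse event summary, three of which the SAP labels a registry reporting requirement, without saying why or where they will be produced

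*SAP*

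**What the plan says.** SAP Version 2.0, Section 7.6.1, Table 7.6.1-1 lists four exposure-adjusted summaries during study therapy: events in at least 5% of subjects, SAEs, related SAEs, and non-serious AEs in at least 5%. The last three, for example "Exposure-adjusted SAEs related to study therapy", carry footnote a, which reads "ClinicalTrials.gov or EudraCT reporting requirement".

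Section 7.6.12 repeats the commitment in the text: "Exposure-adjusted summaries will also be provided for SAEs, SAEs related to study therapy and non-SAEs". It also fixes the metric: "This data will be presented as the rate per 100 years of patient exposure". The Data Presentation Plan, Section 1.2, gives each summary an output number (378 to 385, Tables S.6.6.1A-D and S.6.6.2A-D). The first is titled "Exposure Adjusted Adverse Events Summary Treated Subjects - Stage 1".

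The Final Analysis Appendix, Section 2, opens "Per the company decision to end this study prior to all subjects reaching the primary endpoint". It says that the final analyses "will be performed on subjects who were enrolled into this study, regardless of study stage, and will supersede" the earlier plan. Section 3.3.1 of the appendix then lists the safety displays, numbered 3.1 to 3.46. The AE displays are 3.7 to 3.25, for example "Summary of Serious Adverse Events Modified Treated Subjects".

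**The concern.** Stopping a 96-week study early is the situation in which exposure-adjusted rates are most useful, yet the appendix removes them at that point. A percentage of subjects with an event can be read as a risk only over a stated period. Where subjects are cut off on one calendar date, time on drug depends on entry date and the percentage refers to no particular period.

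Two further losses follow from the SAP's own structure. The dropped related-SAE table was the only planned summary of related SAEs that was not restricted to deaths. The dropped template was also the only AE template that counted events rather than subjects. Separately, three of the dropped outputs carry a label saying that a registry needs them, and the appendix is silent about that label.

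**Working it through.** **The SAP's own rate.** Section 7.6.12 works an example of 7 episodes over 20 patient-years: 7 / 20 x 100 = 35 per 100 patient-years. This reproduces exactly, so the planned metric is clear and computable.

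**Planned summaries against the final list.**

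| Row in Table 7.6.1-1 | Footnote a | Planned output | Final list |
|---|---|---|---|
| Exposure-adjusted events, at least 5% | no | S.6.6.1A, S.6.6.2A | absent |
| Exposure-adjusted SAEs | yes | S.6.6.1B, S.6.6.2B | absent |
| Exposure-adjusted related SAEs | yes | S.6.6.1C, S.6.6.2C | absent |
| Exposure-adjusted non-serious AEs, at least 5% | yes | S.6.6.1D, S.6.6.2D | absent |
| SAEs leading to death | yes | S.6.2.1C, S.6.2.2C | Table 3.9 |
| Related SAEs leading to death | yes | S.6.2.1D, S.6.2.2D | Table 3.10 |
| Non-serious AEs, at least 5% | yes | S.6.5.1A, S.6.5.2A | Table 3.15 |

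Exposure-adjusted outputs: 4 kinds x 2 stages = 8 planned, 0 kept. Footnote-a rows: 6 planned, 3 kept, and the 3 lost are exactly the exposure-adjusted ones.

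**What is left among displays 3.7 to 3.25.** There are 19 items. Five are listings (3.11, 3.12, 3.14, 3.23, 3.25), which leaves 19 - 5 = 14 summary tables. Table 3.7 uses the overall AE template and the other 13 use template GS_AE_T_X_001. Both present numbers and percentages of subjects, and SAP Section 8.6 counts a subject once per preferred term. The event-count template, GS_AE_T_M_001, appears nowhere in the list. Tables 3.19 to 3.21 cover related AEs but do not separate the serious ones, so Table 3.10 is the only summary of drug-related SAEs.

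**Follow-up.** The appendix says that the study ended before all subjects reached the primary endpoint, which is at Week 24. The footnote to Tables 2.2 to 2.4 gives one site-notification date, 10 October 2016. SAP Section 7.6 cuts safety data at database lock, not at an analysis week. Unequal time on drug is therefore likely, but the documents give no entry dates and no observed exposure.

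**Illustration only.** Assume a constant hazard of 0.35 per year, borrowed from the SAP's worked example and not from trial data. The expected share of subjects with at least one event is 1 - exp(-0.35 x weeks x 7 / 365.25):

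- 12 weeks: 7.7%
- 24 weeks: 14.9%
- 48 weeks: 27.5%
- 96 weeks: 47.5%

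The range shows why a percentage needs a time horizon. It is not an estimate of any difference in this trial.

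**The case against.** The strongest reply is that the cut was deliberate. The appendix announces a reduced report and also drops quality-of-life, subgroup and most pharmacokinetic analyses, and text in Version 2.0 that it supersedes cannot by itself convict it. That is fair as to scope. It does not explain why outputs labelled a reporting requirement went while the other three footnote-a rows stayed, and the appendix neither withdraws the label nor points elsewhere.

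The second reply is that the ingredients are still delivered. Table 3.11 lists each SAE in Modified Treated Subjects with its relationship to drug, Listing 10 gives unique events, Listing 8 gives exposure by subject, and Tables 3.1 to 3.6 give time on therapy. This stands in part: nothing is irrecoverable. But Listing 10 is on Treated Subjects, which includes the GCP non-compliant site that the tables exclude, so a reader would have to remove that site and count by hand.

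Three stronger readings are tempting, and the documents do not support them:

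- **That arms differ greatly in time on drug.** Randomisation is 1:1 within Stage 1 and 1:1:1 within Stage 2, so a calendar cut tends to fall alike on the arms of a stage.
- **That comparisons across stages are distorted.** No document shows that any Stage 2 subject was treated. All the AE displays except Table 3.10 map to Stage 1 shells, and the integrated Stage 1 and 2 summaries in SAP Section 7.8 never included exposure-adjusted tables.
- **That a registry obligation will be missed.** Footnote a is the SAP's label. What the registries require, and whether disclosure tables are produced outside this list, is not shown.

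**Conclusion.** The omission is certain and unexplained. All eight exposure-adjusted tables are gone, including every one that the SAP labels a registry requirement. With them go all occurrence counts, all patient-year rates and the only summary of non-fatal drug-related SAEs. The listings and time-on-therapy tables that remain do not replace them.

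The consequence for interpretation is moderate. It rests on the inference, well supported but not quantified in the documents, that stopping on one date left subjects with unequal exposure. The harm lies in reading crude percentages as risks over a defined period. The documents do not support a claim that the randomised contrast within a stage is biased. This should be changed, but it does not threaten the primary efficacy analysis.

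**What to change.** Add the four existing exposure-adjusted shells to Section 3.3.1 of the Final Analysis Appendix, on Modified Treated Subjects: AEs in at least 5% of subjects, SAEs, drug-related SAEs, and non-serious AEs in at least 5%. Each should show event counts, patient-years and rate per 100 patient-years by treatment arm. If any Stage 2 subjects were treated, keep the stages separate by using the S.6.6.2 shells for them. If the sponsor prefers not to restore the tables, the appendix should at least say why and state where the three outputs carrying footnote a will be produced.

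The cost is four more tables in a deliberately short report (up to eight if both stages apply). No new data are needed. The shells are already written, Listing 10 already needs the collapsed unique-event data, and Tables 3.1 to 3.6 already need exposure.
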